5.4.1. Exploratory analyses

Based on PD-L1 analysis set, ORR will be estimated by groups of different PD-L1 expression levels ($PD-L1 \geq 1\%$ vs. $PD-L1 < 1$) (point estimate and 95% CI estimate). The 6/9/12-month survival rate will be estimated by groups of different PD-L1 expression levels (point estimate and 95% CI estimate). BOR will be summarized by the occurrence of capillary endothelial proliferation (with vs. without).

5.4.2. Subgroup analysis

Based on the FAS, subgroup analysis will be conducted merely on OS. The median OS and their 95% CIs will be provided for each subgroup. Forest plot will be prepared when necessary. The definition of subgroup is presented in section 5.1.4.

Based on the FAS, relevant efficacy endpoint analyses will be performed for sub-populations A, B, C, D, and E, with the same analytical method as above. The objective response swimmer plot and survival curves will be plotted for each sub-population.

5.4.3. Other analysis

In accordance with the tumor evaluation by IRC and investigators, the categories of the sum of diameter of the target lesions increased in the first evaluation of tumor response from baseline will be analyzed; the criteria on category are $\geq 100\%$ vs. $\geq 50\%$ and $< 100\%$ vs. $\geq 20\%$ and $< 50\%$ vs. $> 0\%$ and $< 20\%$.

Subjects with initial progression will be classified according to treatment continuation or treatment discontinuation, and the overall duration of treatment (months), overall survival (months), and 6-month survival rate after initial progression will be analyzed. Tumor assessments of subjects who continue treatment beyond investigator-assessed progression will be listed (including subject ID, dose group, assessment visit, date of assessment (presented by the earliest date of occurrence), sum of target lesion diameters and its change (%) from baseline, non-target lesion assessments, presence of new lesions, and the overall assessment). Subjects who continue treatment beyond disease progression and have $> 30\%$ reduction in target lesion relative to baseline (reduction or continuous reduction of target lesion after disease progression) will be listed (subject ID, dose group, largest change in target lesion from baseline (%), duration of treatment after PD (months)). Changes in target lesion from baseline (%) vs. time will be plotted for subjects who continue treatment beyond disease progression.

5.5. Safety Analysis

Unless otherwise specified, the safety analysis will be descriptively summarized and listed by treatment group. All safety analyses will be based on the safety set.

5.5.1. Extent of exposure

The extent of drug exposure will be summarized by duration of drug exposure (months), number of dosing, cumulative dose, and drug intensity mainly for different dose group and overall, using mean, standard deviation, median, maximum, and minimum.

5.5.2. Treatment-emergent adverse events (TEAEs)

Adverse events will be summarized using descriptive statistics according to Hengrui's Statistical Analysis Reporting Standards, including but not limited to:

- Overview of adverse events (all-cause and treatment-related);
- Summary of serious adverse event;
- Incidence and severity of adverse event (all-cause and treatment-related);

- Causality between adverse event and investigational drug;
- Selected related adverse events (endocrine, gastrointestinal, liver, lung, kidney, hypersensitivity/infusion reaction, and skin);
- Adverse events of special interest.

Adverse events of special interest mainly include:

- Hemangioma (time to event and duration of event, outcome, recovery, or remission)
- Grade ≥ 3 infusion reaction
- Grade ≥ 2 diarrhea/colitis, uveitis, and interstitial pneumonia
- Grade ≥ 3 other immune related adverse events: skin, gastrointestinal, lung, endocrine (by system organ class)
- Abnormal hepatic enzyme: abnormal ALT, AST, and total bilirubin from baseline
- Grade 4 amylase or lipase increased

5.5.3. Laboratory evaluations

Baseline is defined as the last measurement prior to first dose. The laboratory data will be summarized using descriptive statistics according to Hengrui's Statistical Analysis Reporting Standards, including but not limited to:

- Incidence of abnormalities by item and parameter;
- Shift table and listing of changes from baseline (normal/abnormal) by item, visit, and parameter;
- Shift table of changes in greatest grade from baseline for parameters that can be graded as per CTCAE.

Laboratory abnormalities will be listed.

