Vital signs	√	√	√	√	Including blood pressure, heart rate, body temperature, respiratory rate. It will be conducted within 72 hours prior to each administration.

Items	Treatment period (One treatment cycle is 42 days)				Comment
	D1 ^[3] (±3 days)	D15 (±3 days) (Group A)	D22 (±3 days) (Group B)	D29 (±3 days) (Group A)	
Concomitant medications/treatments	√	√	√	√	
Collection of AE	√	√	√	√	Including symptoms and signs.
12-Lead ECG					Performed according to local standard during the study, when clinically indicated.
Echocardiography					Performed according to local standard during the study, when clinically indicated.
Hematology	√	√	√	√	Including complete blood cell count and category (white blood cell, red blood cell, lymphocyte, monocyte, neutrophil, basophil, eosinophil, hemoglobin), platelet count. The test will be conducted within 72 hours prior to each administration.
Urinalysis	√	√	√	√	Including white blood cell, red blood cell, and urine protein. The test will be conducted within 72 hours prior to each administration. If urine protein is ≥ 2+, 24 hours urine protein quantification must be detected additionally.
Blood biochemistry	√	√	√	√	Including hepatic function (ALT, AST, TBIL, ALP), renal function (BUN or serum urea level), albumin, creatinine, amylase (lipase must be detected additionally if amylase is abnormal and clinically significant), blood glucose, and LDH. The test will be conducted within 72 hours prior to each administration.
Blood electrolytes	√	√	√	√	Including K ⁺ , Na ⁺ , Ca ⁺⁺ , Mg ⁺⁺ , Cl ⁻ . The test will be conducted within 72 hours prior to each administration.
Coagulation function ^[4]	√				INR and/or PT (if INR cannot be collected, PT will be used as judgment basis). The test will start from Cycle 2, and will be finished at D1 of each cycle.
Alpha fetoprotein ^[4]	√				The test will start from Cycle 2, and will be finished at D1 of each cycle.
Thyroid function ^[4]	√				TSH, FT4 and FT3 will be detected on D1 of each cycle from Cycle 2.
Virology ^[4]	√				The test will start from Cycle 2, and will be finished at D1 of each cycle. HBV-DNA (PCR) will be detected for those with HBV infection; HCV-RNA will be detected for those with HCV infection.

Items	Treatment period (One treatment cycle is 42 days)				Comment
	D1 ^[3] (±3 days)	D15 (±3 days) (Group A)	D22 (±3 days) (Group B)	D29 (±3 days) (Group A)	
Efficacy assessments					

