3.2.2 Treatment period

The treatment period starts from randomization, and the investigational drug must be given within 3 days after randomization.

A cycle is defined as 6 weeks. SHR-1210 3 mg/kg will be given i.v. drip over half an hour, no less than 20 minutes and no more than 60 minutes, including rinsing period, on D1, D15 and D29 of each cycle in Group A, and on D1 and D22 of each cycle in Group B. Physical examination and laboratory examinations will be conducted during treatment, AE and concomitant medications information will be collected.

The following evaluation will be completed within 72 hours prior to each administration of investigational drug in each cycle of therapy:

ECOG PS, physical examination (at least including heart, lungs, abdomen, skin), vital signs, hematology, urinalysis, blood biochemistry, and blood electrolytes examination. The investigational drug can be given only after investigators have reviewed the laboratory test results.

Since the second treatment cycles, the following assessment will be completed at D1 of each cycle:

Coagulation function, alpha fetoprotein, thyroid function (TSH, FT3, FT4), virology (HBV markers or HCV markers), and Child-Pugh class.

In accordance with RECIST v1.1, the initial tumor imaging evaluation is assessed at 8 weeks (± 7 days), and then every 6 weeks (± 7 days), with or without dosing. After 12 months of dosing (i.e., the first dose), if tumor assessment is still required, it should be performed every 12 weeks (± 14 days) until the disease progresses or end of the study (whichever happens later).

The subjects who are evaluated as progressive disease can continue to receive treatment if they meet the criteria defined in Section 3.2.4.

The treatment period will end and proceed to follow-up period when the subjects terminate the study (see Section 5.5).

Note: the specific study procedures during the treatment period are shown in the study flowcharts.

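### Four dose-linked laboratory panels are tested three times per cycle on Q2W and twice on Q3W, so the by-group incidence and greatest-grade tables lean towards more short-lived abnormalities on Q2W

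*SAP*

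**What the plan says.** The Protocol (3.2.2) sets the cycle: "A cycle is defined as 6 weeks". SHR-1210 is given "on D1, D15 and D29 of each cycle in Group A, and on D1 and D22 of each cycle in Group B". Safety assessments follow dosing: "The following evaluation will be completed within 72 hours prior to each administration of investigational drug in each cycle of therapy". The list covers "vital signs, hematology, urinalysis, blood biochemistry, and blood electrolytes examination", and the treatment-period schedule repeats this test by test ("The test will be conducted within 72 hours prior to each administration").

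A second set of tests is not tied to dosing. "Coagulation function, alpha fetoprotein, thyroid function (TSH, FT3, FT4), virology (HBV markers or HCV markers), and Child-Pugh class" are assessed on D1 of each cycle from Cycle 2 in both groups. End-of-treatment tests and the on-site safety visits 30 and 90 days after the last dose are also the same in both groups.

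In SAP 5.5, "the safety analysis will be descriptively summarized and listed by treatment group". SAP 5.5.3 lists three laboratory outputs:

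- incidence of abnormalities by item and parameter;
- a normal/abnormal shift table by item, visit and parameter;
- a "Shift table of changes in greatest grade from baseline for parameters that can be graded as per CTCAE".

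Only the second is tied to visits. SAP 5.1.5 bases summaries on scheduled visits and uses unscheduled ones only to replace missing or invalid results.

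**The concern.** Any-time incidence and greatest grade can only rise as more results are looked at. If one arm is sampled more often, it will on average show more abnormalities and worse maximum grades even when the underlying toxicity is the same. Here the arms differ only in dosing frequency, and sampling frequency moves with it. In these two tables, extra detection on Q2W therefore cannot be separated from extra toxicity.

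Safety is a secondary endpoint (Protocol 2.3). The affected panels include ALT, AST, bilirubin and amylase, which matter in a liver-cancer population. Nothing in the SAP equalises the number of results, restricts these tables to shared visits, or reports how many tests each subject had.

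**Working it through.** **Step 1. Scheduled tests.** The dosing days in Protocol 3.2.2 give, per 42-day cycle, 42/14 = 3 tests on Q2W and 42/21 = 2 on Q3W. Cycle 1 D1 precedes the first dose and is baseline or earlier. Post-baseline tests therefore fall on days 15, 29, … , 169 (Q2W) and 22, 43, … , 169 (Q3W), which is 12 vs 8 by week 24. Adding end of treatment and the two on-site safety visits gives 15 vs 11, a ratio of 15/11 = 1.36.

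**Step 2. Detection under equal toxicity.** The documents give no rate or duration of abnormalities, so both are assumed. Each subject moves between normal and abnormal in the same way in both arms. Onset rate is λ = −ln(1 − I)/168 per day, where I is the true proportion with an episode within 24 weeks (168 days). Episode length is exponential with mean m days. For a subject normal at the previous test d days earlier, the chance of an abnormal next test is

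p(d) = [λ/(λ + 1/m)] × [1 − exp(−(λ + 1/m)d)]

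and the chance of at least one abnormal result in k tests is 1 − (1 − p)^k. End-of-treatment and follow-up visits are left out.

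**Step 3. Worked case, I = 20%, m = 7.** λ = 0.2231/168 = 0.001328; λ + 1/m = 0.14419; λ/(λ + 1/m) = 0.00921.

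- Q2W: p(14) = 0.00921 × (1 − e^(−2.019)) = 0.00799; 1 − (1 − 0.00799)^12 = 9.2%.
- Q3W: p(21) = 0.00921 × (1 − e^(−3.028)) = 0.00877; 1 − (1 − 0.00877)^8 = 6.8%.

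**Step 4. Range of durations, I = 20%.**

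| Mean duration | Q2W | Q3W | Ratio |
|---|---|---|---|
| 3 days | 4.6% | 3.1% | 1.48 |
| 7 days | 9.2% | 6.8% | 1.35 |
| 14 days | 13.1% | 10.9% | 1.21 |
| 28 days | 16.1% | 14.5% | 1.11 |
| 84 days | 18.6% | 17.9% | 1.04 |
| permanent | 20.0% | 20.0% | 1.00 |

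For 7-day episodes, I = 10% gives 4.4% vs 3.3% and I = 40% gives 19.7% vs 14.8%.

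**Step 5. Size against noise.** With 220 randomized 1:1, each arm has about 110 subjects. In the worked case the difference is 2.4 points and its standard error is √[(0.092 × 0.908 + 0.068 × 0.932)/110] = 3.7 points. By normal approximation, Q2W would show the higher observed rate in about 74% of trials. Across all scenarios run (I of 10%, 20% and 40%, all durations above) this ranges from 50% (permanent) to about 83% (I = 40%, 7-day).

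**Step 6. Common visits only.** D1 of Cycles 2 to 5 (days 43, 85, 127, 169) gives four tests in each arm, 42 days apart. In the worked case both arms detect 3.6%, so the expected difference is zero. The price is lower detection than the 9.2% and 6.8% from all scheduled tests.

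**The case against.** The strongest reply is that the plan already holds a fair comparison. The by-visit normal/abnormal shift table can be read across arms at D1 of each cycle, end of treatment and the safety visits, and the number of doses is reported by group (SAP 5.5.1), which shows the imbalance indirectly. This stands, so it would be wrong to say that the by-visit tables do not help. But that table is neither graded nor cumulative, and its D15, D29 and D22 entries have no counterpart in the other arm. It does not replace a like-for-like greatest-grade or incidence table.

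SAP 5.5.3 also defers to the sponsor's reporting standards, which are not among the documents and might contain a relevant rule. And it does not say whether greatest grade uses unscheduled results. If it does, the weekly monitoring during dose delay (Protocol 7.2.2) would change the size of the bias.

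Three stronger readings are tempting, and the documents do not support them:

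- *Q2W will show more laboratory toxicity.* The bias is in expectation, confined to four panels, small from about four weeks' duration, and nil for permanent abnormalities.
- *The gap is about 10 points.* An independent 5% chance per test with 9 vs 6 tests gives 1 − 0.95^9 = 37.0% vs 1 − 0.95^6 = 26.5%. Strictly, three cycles hold 8 vs 5 post-baseline tests, giving 33.7% vs 22.6%. Either way, the 5% is not in the documents, and repeated values in one subject are not plausibly independent.
- *The choice of regimen would rest on this artefact.* No regimen-selection rule appears. The success criteria use overall confidence intervals (SAP 3), safety is descriptive, and phase III has a separate protocol.

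Descriptive status limits the consequences but does not remove the bias.

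**Conclusion.** The point holds for hematology, biochemistry, electrolytes and urinalysis, in two tables of SAP 5.5.3: any-time incidence and greatest-grade shift. The 3 vs 2 testing ratio comes directly from the Protocol, and the visible SAP text does not correct for it. The direction of the bias, towards more short-lived abnormalities on Q2W, follows from the schedule.

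Its size rests on assumed incidence and duration. At 20% true incidence, detection is inflated by a factor of roughly 1.2 to 1.5 for episodes of two weeks or less, about 1.1 at four weeks, and not at all for permanent abnormalities. At about 110 per arm this is often within sampling noise. Summaries pooled over both arms raise no between-arm issue. The change is worth making because it is cheap and removes an avoidable ambiguity, not because the tables are certain to mislead.

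**What to change.** In SAP 5.5.3, for the four dose-linked panels:

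1. Add by-group incidence and greatest-grade shift tables restricted to visits common to both arms: D1 of each cycle after Cycle 1, end of treatment, and the on-site safety visits.
2. Keep the all-results tables and footnote the 3:2 scheduled testing ratio.
3. Report the number of tests per subject by group.
4. State whether unscheduled results count towards greatest grade.

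The cost is one extra set of tables, with no change to any visit. The new tables miss more transient peaks. They are also not a perfect match, because D1 falls 14 days after the last dose on Q2W and 21 days after on Q3W. Equal numbers of common visits also depend on similar time on treatment, which the count of tests per subject will show. For these reasons they should supplement the full tables, not replace them.

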5.5.4. Vital signs

Baseline is defined as the last measurement prior to first dose. Vital signs will be summarized using descriptive statistics according to Hengrui's Statistical Analysis Reporting Standards, including but not limited to: descriptive summaries of absolute value and change from baseline at the scheduled visits in the protocol.

5.5.5. Electrocardiogram

The listing of ECG results will be provided.

5.5.6. Physical examination

Physical examination results will be summarized using descriptive statistics according to Hengrui's Statistical Analysis Reporting Standards, including but not limited to: descriptive summary of absolute value at the scheduled visits in the protocol.

5.5.7. Other safety measures

The ECOG PS at baseline and change from baseline will be analyzed by visit and group. Child-Pugh score will be summarized by visit and group (as continuous variable), and analyzed for frequency and percentage (as categorical variable).

The listing of echocardiography results will be provided.

The categories of the greatest post-baseline HBV-DNA values (< 500 , $500-2000$, and ≥ 2000 IU/mL) will be summarized. The proportion of subjects with ≥ 100 -fold ($2\log_{10}$) maximum change in the greatest post-baseline HBV-DNA values relative to baseline will be summarized and the maximum rate of change from baseline will be descriptively summarized. AEs and efficacy in subjects with post-baseline HBV-DNA ≥ 2000 IU/mL will be summarized.

5.6. Pharmacokinetic Analysis

None.

5.7. Pharmacodynamics Analysis

None.

6. REFERENCES

None.

7. APPENDIX

None.
